#### **8.10.1 FACT-GP5**

The FACT-GP5 ("I am bothered by side effects of treatment") is a single-item from the Functional Assessment of Cancer Therapy-General (FACT-G) scale (63). Responses are given on a 5- point Likert-type scale recalling the past 7 days. Higher scores indicate a higher degree of side effect bother (64). The FACT-GP5 has been translated in over 50 languages according to a standardized translation procedure (65).

#### **8.10.2 EORTC QLQ-30**

The EORTC Quality of Life Questionnaire (QLQ-C30) version 3 (66) is valid for any cancer population and is composed of thirty distinct questions that are scored into fifteen multi-item and single-item scales (67). These include a global health status/QoL scale (2 items), five functional scales (physical functioning (5 items), role functioning (2 items), emotional functioning (4 items), cognitive functioning (2 items), and social functioning (2 items)); eight symptom scales (fatigue (3 items), nausea and vomiting (2 items), pain (2 items), dyspnoea (1 item), insomnia (1 item), appetite loss (1 item), constipation (1 item), diarrhoea (1 item)); and a financial difficulties scale (1 item). The questionnaire employs 28 4-point Likert-type scales with responses from "not at all" to "very much" and two 7-point Likert-type scales for global health and overall QOL. For functional and global QOL scales, higher scores represent a better level of functioning and are converted to a 0 to 100 scale. For symptom-oriented scales, a higher score represents more severe symptoms. The reliability and validity of the questionnaire is highly consistent across different language-cultural groups (68, 69). The average time to complete the questionnaire is approximately 10 minutes. The EORTC QLQ-C30 version 3 has been translated in over 50 languages according to a standardized translation procedure (70).

### 8.10.3 EORTC QLQ-BR23

The EORTC QLQ breast cancer module (QLQ-BR23) is a 23-item disease-specific patient-reported outcome measure of disease-related symptoms, treatment-related symptoms, and functioning relevant to patients with breast cancer. The QLQ-BR23 has been validated for use in conjunction with the QLQC30 (68, 71). The QLQ-BR23 consists of 23 4-point Likert scales with responses from “not at all” to “very much” which are scored into both multi-item scales and single-item scales, including: four functional scales (body image (4 items), sexual functioning (2 items), sexual enjoyment (1 item), and future perspective (1 item)); and four symptom scales (systemic therapy side effects (7 items), breast symptoms (4 items), arm symptoms (3 items), upset by hair loss (1 item)). The scoring principle is similar to the QLQ-C30 (67) with higher scores on the functional scales indicating higher levels of functioning and higher scores on the symptom scales indicating higher symptom levels. The average time to complete the questionnaire is approximately 10 minutes. The EORTC QLQ-BR23 has been translated in over 50 languages according to a standardized translation procedure (70).

### 8.10.4 EORTC QLQ-IL127

In addition to the QLQ-C30, the EORTC Item Library (72) was used to construct an ad-hoc item list specific to this study. The aim was to add items from the EORTC CAT physical functioning questionnaire (68) in order to obtain an extended, more precise physical functioning scale. A total of 3 items were selected to include self-assessment on physical functioning:

1. Do you have any trouble carrying a heavy bag upstairs?
2. Do you have any trouble taking a long walk carrying a heavy pack on your back (eg, a filled rucksack)?
3. Do you have any trouble hiking 3 km/2 miles on uneven surfaces?

These questions are taken from the validated QLQ-CAT physical functioning questionnaire. Although this Item List is not a validated instrument, it is an ad-hoc instrument optimized for this specific setting and composed of integral parts of validated HRQL questionnaires. All three questions follow the same structure using a 4-point Likert scales with responses from “not at all” to “very much” and are translated according to a standardized translation procedure (72). These three questions will be scored together with the 5 physical functioning items of the QLQ-C30 according to the CAT scoring procedure into an extended physical functioning scale.

### 8.10.5 PRO-CTCAE

The National Cancer Institute PRO-CTCAE™ was developed to evaluate symptomatic adverse events (AEs) by self-report among patients participating in cancer clinical trials (73, 74). The PRO-CTCAE item library includes 124 items that represent 78 symptomatic AEs in the clinician reported CTCAE. PRO-CTCAE items chosen for this study were systematically selected from the PRO-CTCAE item library to measure 14 symptomatic AEs (representing 24 items) known to be associated with amcnestrant and/or tamoxifen. PRO-CTCAE items included in this study assess the frequency, severity, interference, and/or presence/absence of the following 14 symptomatic AEs: hot flashes (2 items; frequency and severity); increased sweating (2 items; frequency and

severity); joint pain (3 items; frequency, severity, interference), muscle pain (3 items; frequency, severity, interference); fatigue (2 items; severity, interference); vaginal dryness (1 item; severity); vaginal discharge (1 item; presence/absence); irregular periods/vaginal bleeding (1 item; presence/absence); nausea (2 items; frequency, severity); vomiting (2 items; frequency, severity); diarrhea (1 item; frequency); constipation (1 item; severity); decreased appetite (2 items; severity, interference); rash (1 item; presence/absence). PRO-CTCAE frequency, severity, and interference items use a 5-point Likert-type response scale respectively ranging from "never" to "almost constantly", "none" to "very severe", and "not at all" to "very much" (each scored from 0 to 4, with higher scores indicating a higher frequency, severity, or interference of the given symptomatic AE) (75). PRO-CTCAE presence/absence items use a dichotomous "no"/"yes" response scale (scored 0 and 1, respectively) (75).

In accordance with scale developer recommendations (76), conditional branching will be employed for the electronic administration of PRO-CTCAE symptom terms that have two or more items to reduce respondent burden. The logic branches from frequency, then to severity, then to interference. Using the joint pain items as an example: if a given respondent reports the frequency of joint pain is greater than "Never", the respondent will be administered the severity item; if the respondent reports severity of joint pain is greater than "None", the respondent will be administered the interference item. Using conditional branching in electronic PRO-CTCAE item administration, participants will be administered a minimum of 14 items and a maximum of 24 items, depending upon their responses.

Items from the PRO-CTCAE item library were selected in accordance with recommendations by the FDA (77, 78) and using methods informed by the published literature (79, 80). See Section 10.10.2 (Appendix 10) for detailed item selection methods.

#### **8.10.6 MMAS-8**

The Morisky Medication Adherence Scale (MMAS-8) is a validated assessment tool used to measure non-adherence in a variety of patient populations (81). It has proved to be a valuable resource to address adherence concerns, such as forgetting to take medications or discontinuing medications without guidance. If a patient scores higher on the scale, they are evaluated as more adherent. If they score lower on the scale, they are presumed to be struggling with nonadherence. By understanding how the patient scored on the scale, clinicians and health organizations can identify underlying issues that prevent patients from taking their medications correctly, if at all.

#### **8.10.7 PGI-S and PGI-C**

The Patient Global Impression scale (PGI), also known as Subject Global Impression (SGI), is the PRO counterpart to the Clinical Global Impressions scale, (CGI), which was published in 1976 by the US National Institute of Mental Health (82). Over the years, PGI scales were used in a broad range of diseases and were modified for the purpose of clinical settings. In this study, the PGI-S and PGI-C each consist of one item based on the CGI and adapted to the current setting. The PGI-C measures change in side effects of treatment over time; while the PGI-S measures severity in side effects of treatment at the time of assessment.

### **8.10.8 EUROQoL EQ-5D-5L**

The EQ-5D-5L is a standardized, self-rated measure of health status developed by the EuroQoL Group (83) that is designed to provide a utility score suitable for use in health economic evaluations. It provides a descriptive classification based on self-assessment of 5 domains (84): mobility, self-care, usual activities, pain/discomfort, and anxiety/depression using a 5-level rating scale of no problems, slight problems, moderate problems, severe problems and extreme problems. These scores are combined to obtain discrete health states which can be assigned index values reflecting how good or bad a health state is according to the preferences of the general population of a country/region. In addition, it contains a self-rating of health on a vertical visual analogue scale from ‘the best health you can imagine’ to ‘the worst health you can imagine’ scored on a 0-100 scale. The EQ-5D-5L is available in more than 150 languages with all translations produced using a standardized translation protocol that conforms to internationally recognized guidelines (85).

## 9 STATISTICAL CONSIDERATIONS

### 9.1 POPULATIONS FOR ANALYSES

The following populations are defined (Table 6):

**Table 6 - Populations for analyses**

Population	Description
Screened	All participants who signed the ICF.
Randomized	All participants from screened population who have been allocated to a randomized intervention by IRT regardless of whether the intervention was received.
Intent-to-treat (ITT)	All randomized participants. Participants will be analyzed according to the intervention allocated by randomization.
Safety	All randomized participants who took at least 1 dose of study intervention. Participants will be analyzed according to the intervention they actually received.
PK population	All randomized and treated participants (safety population) with at least one post-baseline PK concentration with adequate documentation of dosing and sampling dates and times. Participants will be analyzed according to the intervention they actually received.

Participants exposed to study intervention before or without being randomized will not be considered randomized and will not be included in any analysis population. The safety experience of these participants will be reported separately.

Randomized participants for whom it is unclear whether they took the study intervention will be considered as exposed and will be included in the safety population as randomized.

### 9.2 STATISTICAL ANALYSES

The statistical analysis plan (SAP) will be finalized before the first database lock and will include a more technical and detailed description of the statistical analyses described in this section. This section is a summary of the planned statistical analyses of the most important endpoints including primary and secondary endpoints.

#### 9.2.1 General considerations

The baseline value is defined as the last available value before randomization, unless otherwise specified.

Unless otherwise specified, analyses will be performed by intervention group (and overall for baseline and demographics characteristics).

The observation period will be divided into 3 segments:

- The **pre-treatment period** is defined as the period up to first IMP administration.

- The **on-treatment period** (ie, treatment-emergent (TE) period) is defined as the period from the first IMP administration to the last IMP administration + 30 days.
- The **post-treatment period** is defined as the period from the end of the on-treatment period.

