NIMP: GnRH analog		↔							- Goserelin or other GnRH analog approved for use in early breast cancer as per site/ country availability - In men and pre/perimenopausal women

Procedure	Screening Period	Treatment Period [5 years – C1-C65]					EOT	Follow-up Period	Notes
		0	1	2	3	4-10 Q12 weeks			
Patient Visit #	Baseline	C1 D1	C2 D1	C4 D1	C7, C10, C13, C16, C19, C22, C25 D1	C28, C34, C40, C46, C52, C58 D1	D30 after last IMP dose	Q12 months after last IMP dose	
Patient Cycle Visit #	Up to 28 days before randomization	±3	±3	±7	±7	±7	±7	±45	
AE/SAE review	←=====→							X (ongoing related AEs, AESI, ongoing SAEs at EOT and new related AE/SAEs)	
Concomitant medication review	←=====→							X (related to AE/SAEs listed above)	From the date of informed consent form up to 30 days after the last dose of study treatment
Disease assessments:									
Disease recurrence assessment	X								At every visit and as clinically indicated until the detection of locoregional recurrence and distant recurrences (whichever comes last) or end of follow-up period, whichever comes first.

Procedure	Screening Period	Treatment Period [5 years – C1-C65]					EOT	Follow-up Period	Notes
		0	1	2	3	4-10 Q12 weeks			
Patient Visit #	Baseline	C1 D1	C2 D1	C4 D1	C7, C10, C13, C16, C19, C22, C25 D1	C28, C34, C40, C46, C52, C58 D1	D30 after last IMP dose	Q12 months after last IMP dose	
Patient Cycle Visit #	Up to 28 days before randomization	±3	±3	±7	±7	±7	±7	±45	
Time Window (day)									
Mammogram	X a				X b				
a. Screening: to be done if not already done in the past 6 months prior to randomization.
 
If local investigator plans to use MRIs instead of mammograms during the study, MRI will have to be performed at baseline
 
b. Post baseline: yearly from randomization (±30 days), and as clinically indicated until the detection of locoregional recurrence and distant recurrences (whichever comes last) or end of follow-up period, whichever comes first.

Procedure	Screening Period	Treatment Period [5 years – C1-C65]					EOT	Follow-up Period	Notes
		0	1	2	3	4-10 Q12 weeks			
Patient Visit #	Baseline	C1 D1	C2 D1	C4 D1	C7, C10, C13, C16, C19, C22, C25 D1	C28, C34, C40, C46, C52, C58 D1	D30 after last IMP dose	Q12 months after last IMP dose	
Patient Cycle Visit #	Up to 28 days before randomization	±3	±3	±7	±7	±7	±7	±45	
Time Window (day)									

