Time Window (day)		X a	X a				X b		Refer to Section 8.6.2 for details a. Pre-dose b. Collected at EOT for patients who discontinued treatment due to disease recurrence
(Optional) Blood Samples for Future Research									

All study visits performed during treatment period and follow-up period are conducted on-site (in participants without disease recurrence). On-site visits could be substituted by remote visits in specific circumstances.

**Screening:** Routine baseline tests performed prior to ICF signature do not need to be repeated as long as they are within the screening defined timeframe. Informed consent should be signed before any study specific procedures. It can be signed more than 28 days prior to randomization. Screening time indicates in which timeframe exams used to support eligibility have to be done prior to randomization.

**Randomization:** To take place once the consented patient has completed all the necessary screening procedures and is deemed eligible for study entry by the Investigator or designee. All eligible patients must be randomized using IRT. Every effort should be made to start treatment within 3 working days of randomization.

**Treatment period:** A cycle is defined as a 28-day period. Men and pre/perimenopausal women will receive GnRH analog on D1 of the cycle.

**Physical examination/ signs and symptoms evaluation:** At a minimum, assessments of the cardiovascular system, pulmonary system, gastrointestinal system (including palpation of liver and spleen), examination of the skin, and breast exam (palpation of breast/chest wall, axillae, supra- and infraclavicular regions). Symptom-directed physical examinations should be performed at screening and at each subsequent visit.

**Cycle 1 D1** refers to the day the patient receives the initial dose of IMP. Repeated evaluation of body weight, signs and symptoms, physical examination and laboratory tests is not necessary if performed within 7 days prior to 1st IMP administration. If evaluation performed during screening is abnormal, repeated evaluation is recommended within 2 days prior to 1st IMP administration.

**End of treatment (EOT):** should be performed 30 days (±7 days) after the last IMP and prior to the initiation of any new anti-cancer therapy, whichever comes first.

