## 4 STUDY DESIGN

### 4.1 OVERALL DESIGN

This is a prospective, randomized, international, multicenter, double-blind, double-dummy, Phase 3 study comparing the efficacy and evaluating the safety of amcnestrant *versus* tamoxifen.

The study will have 3 main periods: screening, active treatment, and follow up.

Men, pre/peri-menopausal women (with GnRH analog approved for use in early breast cancer) and post-menopausal women with HR+ early breast cancer, who have discontinued adjuvant AI therapy due to treatment-related toxicity will enter the screening period to assess their eligibility.

**Participants still on AI treatment may enter the screening period for central confirmation of biomarkers and screening imaging assessments. The other assessments/questionnaires required before randomization will be performed/completed when patient is off the AI therapy.**

All eligible participants for whom ER and PgR status have been centrally confirmed will be randomly assigned using an IRT to either amcnestrant 200 mg daily (experimental) arm or tamoxifen 20 mg daily (control) arm in a 1:1 ratio.

- Arm A: Amcnestrant 200 mg + tamoxifen-matching placebo
- Arm B: Amcnestrant-matching placebo + tamoxifen 20 mg

All randomized patients will also receive the matching placebo of the other treatment under evaluation. Both treatments are given orally.

The study population will be stratified by the following factors, as reported at the time of randomization:

- Prior exposure to (neo)adjuvant AI therapy:  $\leq 12$  months vs.  $> 12$  months
- Prior exposure to (neo)adjuvant chemotherapy and HER2 status: HER2-negative breast cancer with NO prior (neo)adjuvant chemotherapy vs. HER2-negative breast cancer with prior (neo)adjuvant chemotherapy vs. HER2-positive breast cancer with prior (neo)adjuvant chemotherapy

Note: Participants with unknown HER2 status will be classified as HER2-negative.

- Prior exposure to CDK4/6 inhibitor (Yes or No)
- Geographic regions (North America, Europe vs. Asia Pacific vs. Other)
- Men or peri-/pre-menopausal women vs. post-menopausal women

During the treatment period, men and pre/perimenopausal women will receive GnRH analogs as approved in the respective countries.

Participants will receive their assigned treatment for the planned duration of 5 calendar years or until diagnosis of disease recurrence per IBCFS definition or any other withdrawal criterion whichever occurs first.

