### **8.1.3 Overall survival follow-up**

After discontinuation of study treatment, follow-up visits will be performed every 12 months (±45 days) from the last dose of study treatment for survival status and collection of data on post-study anticancer therapies, and disease recurrence for patients who complete or prematurely discontinue study treatment without disease recurrence.

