#### **9.2.5 Safety analysis**

##### **9.2.5.1 Adverse events**

#### **General common rules for adverse events**

The AEs will be analyzed in the following 3 categories:

- Pre-treatment AEs: AEs that developed, worsened or became serious during the pre-treatment period.
- TEAEs: AEs that developed, worsened or became serious during the treatment-emergent period.
- Post-treatment AEs: AEs that developed, worsened or became serious during the post-treatment period.

Similarly, the deaths will be analyzed in the pre-treatment, treatment-emergent and post-treatment periods.

TEAEs will be coded according to MedDRA. Adverse events will be graded according to the NCI-CTCAE v5.0. The grade will be taken into account in the summary. For participants with multiple occurrences of the same preferred term (PT), the maximum grade will be used.

Summaries will be provided for all grades combined and for Grade  $\geq 3$  (including Grade 5). Missing grades, if any, will be included in the “all grades” category.

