### **9.2.5.2 Laboratory variables, vital signs and electrocardiograms (ECGs)**

#### **Analyses according to PCSA and NCI grading**

For laboratory variables, analyses according to NCI grading will be made based on NCI-CTCAE version 5.0. In addition, for laboratory variables for which NCI-CTCAE scale is not applicable, vital signs and ECG variables, PCSA analyses will be performed based on the PCSA list currently in effect at Sanofi at the time of the database lock.

Analyses according to PCSA and NCI grading will be performed based on the worst value during the treatment-emergent period, using all measurements (either local or central, either scheduled, nonscheduled or repeated).

For laboratory variables, vital signs and ECG variables, the incidence of participants with at least one PCSA during the treatment-emergent period will be summarized regardless of the baseline level and according to the following baseline status categories:

- Normal/missing
- Abnormal according to PCSA criterion or criteria

For laboratory variables graded by NCI-CTCAE.

- The number (%) of participants with abnormal laboratory tests at baseline will be presented by grade.
- The number (%) of participants with abnormal laboratory tests during the treatment-emergent period will be summarized by grade. When appropriate, the number (%) of participants with abnormality of any grade and with Grade 3-4 abnormalities will be provided.

For ECG, the incidence of participants with at least one abnormal ECG during the treatment-emergent period will be summarized regardless of the baseline level and according to the following baseline status categories:

- Normal/missing
- Abnormal

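### The treatment-emergent window is neither cut nor flagged when new anticancer therapy starts, so next-line toxicity can enter the safety tables that ignore causality

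*Combined protocol and SAP*

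**What the plan says.** - **Analysis window.** Section 9.2.1: the on-treatment (treatment-emergent) period "is defined as the period from the first IMP administration to the last IMP administration + 30 days". Section 9.2.5.1 defines TEAEs by that window alone, as "AEs that developed, worsened or became serious during the treatment-emergent period", and splits deaths by the same periods.
- **Laboratory, vital signs, ECG.** Section 9.2.5.2 grades the worst value in the window, "using all measurements (either local or central, either scheduled, nonscheduled or repeated").
- **When study drug stops.** Section 4.1: treatment continues for five years or "until diagnosis of disease recurrence per IBCFS definition or any other withdrawal criterion".
- **End-of-treatment visit.** The notes to the schedule of activities (Section 1.3) say that it "should be performed 30 days (±7 days) after the last IMP and prior to the initiation of any new anti-cancer therapy, whichever comes first".
- **AE collection.** Section 8.3.1 collects all AEs and SAEs to at least 30 days after the last study intervention. The follow-up column of the schedule of activities, which applies after the end-of-treatment visit, lists only "ongoing related AEs, AESI, ongoing SAEs at EOT and new related AE/SAEs".
- **Tables.** Section 9.2.5.1 plans tables of all TEAEs, serious TEAEs and IMP-related TEAEs, among others, with summaries for all grades and for Grade ≥3.
- **Later therapy.** Section 8.1.3 provides for "collection of data on post-study anticancer therapies".

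**The concern.** Recurrence ends study drug and is also when replacement systemic treatment is most likely to begin. The 30 days after the last dose can therefore contain the first weeks of a different and possibly more toxic treatment. The plan recognises this for the visit schedule, by placing the end-of-treatment visit before new therapy. It also recognises it for efficacy: Table 8 states how new therapy before an IBCFS event is handled. The safety analysis has no counterpart.

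The amount of such toxicity depends on the efficacy outcome. If amcenestrant reduces recurrence as designed, the tamoxifen arm has more participants moving to next-line therapy and more events from it, which would flatter amcenestrant. Table 1, in its entry on eye disorders, expects few Grade ≥3 events, and in a sparse table small additions show most.

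**Working it through.** **1. What the text allows.** Take a participant whose recurrence ends study drug on day 0 and who starts systemic therapy on day 14.

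- Under Section 8.3.1, a new AE on day 20 is collected. By Sections 9.2.1 and 9.2.5.1 it is a TEAE and enters every table that has no causality filter.
- Under the schedule of activities, the end-of-treatment visit falls before day 14. After it, a new AE judged unrelated to study drug is not on the collection list, so it would be missing although the analysis window is still open.
- A death on day 25 is recorded under either reading, because survival is followed, and is treatment-emergent by date alone.
- A laboratory value on day 20 counts towards the worst grade if it reaches the database.

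The two collection rules agree when the end-of-treatment visit is at day 30. They diverge when it is brought forward, which is the case at issue.

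**2. The plan's event figures, reproduced.** Inputs from Sections 9.3 and 9.4: HR 0.76, one-sided 2.5%, 90% power, 4-year tamoxifen IBCFS 82%, dropout 1% per year, 1869 per arm, Table 12 accrual.

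- Schoenfeld: 4(1.960 + 1.282)² / (ln 0.76)² = 559 events. Freedman: 566. The plan has 568.
- Two-look O'Brien-Fleming spending at information 0.75 and 1: nominal p 0.0096 and 0.0221, HR bounds 0.7971 and 0.8447, power 68.9% at the second interim and 90.0% overall. These match Table 11.

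**3. Events by arm.** Monthly hazards: tamoxifen λ = −ln(0.82)/48 = 0.00413; amcenestrant 0.76λ = 0.00314; dropout δ = −ln(0.99)/12 = 0.00084. For entry at month s, the probability of an observed event by month 60 is [λ/(λ+δ)] × [1 − exp(−(λ+δ)(60−s))], averaged over the Table 12 accrual and multiplied by 1869.

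- Both arms together: 188.7 events at month 28, 426.5 at 47.5 and 568.3 at 60 (plan: 189, 426, 568).
- By arm at month 60: tamoxifen 319.7 (17.1% of 1869), amcenestrant 248.5 (13.3%).

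**4. Ceiling.** If every IBCFS event, including deaths and events off study drug, put one otherwise uncounted participant into a table, the between-arm difference would be (319.7 − 248.5)/1869 = 3.8 percentage points.

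**5. Range.** Three fractions are needed, and the documents give none of them. Assumed: f, the share of events that are non-fatal recurrences on study drug, 50–90%; s, the share of those starting new therapy within 30 days, 30–90%; q, the share of those with an event not already counted in that table, 10–60%. Excess per arm = event percentage × f × s × q.

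| Scenario | f × s × q | Tamoxifen | Amcenestrant | Difference |
|---|---|---|---|---|
| Low | 0.50 × 0.30 × 0.10 = 0.015 | 0.26% (5) | 0.20% (4) | 0.06 points |
| Middle | 0.70 × 0.60 × 0.30 = 0.126 | 2.16% (40) | 1.68% (31) | 0.48 points |
| High | 0.90 × 0.90 × 0.60 = 0.486 | 8.31% (155) | 6.46% (121) | 1.85 points |

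Participants are in parentheses. This sizes only therapy started after recurrence. Switches to other treatment after stopping for another reason are not sized.

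**The case against.** A reader might infer that toxicity of post-recurrence treatment is always tabulated as study-drug toxicity. The documents do not support that, for these reasons:

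- An all-TEAE table ignores causality by design. The table that attributes toxicity is the IMP-related one, and Section 10.3.3 has the investigator weigh concomitant therapy as an alternative cause. Tables of TEAEs leading to discontinuation or dose modification are largely protected, because study drug has already stopped.
- On the schedule-of-activities reading, new unrelated AEs after an early end-of-treatment visit are not collected and cannot be tabulated.
- The laboratory route is narrow. Scheduled tests end at the end-of-treatment visit. Under Section 8.2.3, local results outside the protocol are recorded only if they change management or are clinically significant.
- Tables count participants with at least one event, so anyone already counted adds nothing.
- Truncation has an arm-dependent cost of its own. Section 10.4 derives 160 days for male contraception as five tamoxifen half-lives plus 90 days, which implies 160 − 90 = 70 days of relevant tamoxifen exposure. The whole 30-day tail lies within it, so cutting the window drops some genuine delayed tamoxifen events, more often in the arm with more recurrences.
- Section 9.2 calls itself a summary and defers detail to a SAP. No separate SAP text was available for this review.

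Most of this stands, and it limits the point to a possible distortion of certain tables. It also argues against making the truncated window the only one. It does not remove the gap: no text reviewed cuts or flags data after new therapy, and Section 9.2.1 gives an explicit definition that a SAP would normally inherit. The collection objection exposes a further inconsistency, because under that reading ascertainment stops before the analysis window does.

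**Conclusion.** The point holds in a limited form. As written, the window runs to 30 days after the last dose whatever is given next. Under Section 8.3.1, data arising after next-line therapy starts can enter the all-TEAE, serious, Grade ≥3, death and worst-grade laboratory tables, but not automatically the IMP-related table.

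If recurrences differ as designed, more of this falls on tamoxifen. The difference is about 0.06 to 1.85 percentage points under the assumed ranges, and at most 3.8 at month 60 by the recurrence route. With equal recurrence in the two arms the expected imbalance from this route disappears, although both arms would still carry some of these events. A reader might infer a large bias in the safety comparison; the documents give no timing of next therapy and so cannot support that. What they do support is a distortion that depends on outcome, has a predictable direction under the design assumptions, and would go unseen in the planned tables.

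**What to change.** 1. Keep last dose + 30 days as defined. Flag every AE, death, and laboratory, ECG or vital-sign value dated on or after the start of new systemic anticancer therapy, and define that term in the SAP.
2. Prespecify parallel tables in which the window ends at the earlier of last dose + 30 days and the day before that start. Either version may be primary, but both must be shown.
3. Reconcile the end-of-treatment note and the follow-up AE list in the schedule of activities with Section 8.3.1, so that collection covers the whole analysis window when the end-of-treatment visit is early.

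**Cost.** Items 1 and 2 need only analysis definitions and programming. Section 6.8 already asks for start and end dates of medication received during the study, and Section 8.1.3 covers later anticancer therapy; the sponsor should confirm that the follow-up form captures the start date. Item 3 is a wording change to the protocol with a reminder to sites. The truncated tables move some delayed study-drug events to the post-treatment period, which is why the uncut tables stay beside them.
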